5.3 Concomitant Medication

To date, there are no known drug-drug interactions for H01. Metoclopramide, its derivatives and morphine are cited in one product label as potentially reducing the effect of H01.

Participants can remain on an FDA approved PAH/PH background therapy if they have been on a stable regimen for a minimum of 90 days prior to randomization.

Participants on a supportive therapy (e.g., anticoagulants, diuretics, oxygen) must have been on a stable and optimized dose for at least 30 days prior to the first dose of study drug. Exceptions are the discontinuation or dose changes of anticoagulants and / or dose change of diuretics. Participants on a chronic medication for underlying lung disease should be on a stable and optimized dose for > 30 days prior to the first dose of study drug.

Participants may not newly initiate PAH/PH treatment from the first dose of study drug (Baseline) through study termination. Participants may not initiate pulmonary rehabilitation (rehab) within 90 days prior to the first dose of study drug and until the end of the study.

All concomitant medications taken during the conduct of the study, including those taken for AEs or other medical events, should be recorded in the subject's source documents and transcribed into the eCRF as required.

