6 SCHEDULE OF ASSESSMENTS

Schedule of Assessments for SATURN Trial

Visits	Screen		Active							FU			
	Screening	Baseline	Week 2	Week 4	Week 8	Week 12	Week 16	Week 20	Week 24	Week 26**	Week 28+	Week 36**	Week 48 **
Day ^a	0	1	14±3	28±3	56 ± 3	84±7	140 ± 7	168±7	196±7	210±3	224±3	280±7	364±7
Telephone or Email Contact			x		x		x	x		x**	x^	x**	
Informed Consent	x												
History and physical													
Medical history	x	x											
Symptom assessment/NYHA	x	x	x	x	x	x	x	x	x	x**	x+	x**	x**
Medications	x	x	x	x	x	x	x	x	x	x**	x+	x**	x**
Vital Signs & Weight	x		x		x			x			x**		x**
Physical Examination	x		x		x			x			x**		x**
EMPHASIS-10 / SGQ	x		x		x			x			x**		x**
General Testing													
Comprehensive Metabolic Panel	x		x		x			x		x	x**		x**
CBC	x		x		x			x		x	x**		x**
Pregnancy test (If Indicated) ^a	x		x	x*	x	x*	x*	x*	x	x**	x**	x**	x**
12-Lead ECG	x												
Endpoint assessment													
Right Heart Catheterization	x								x				
Serum & EBC hyaluronan	x		x		x			x		x	x**		x**
6 minute walk distance	x		x		x			x		x	x**		x**
NT-pro-BNP	x		x		x			x		x	x**		x**
PFT with ABG	x							x		x			
Inflammatory markers	x		x		x			x		x	x**		x**
Serum and EBC drug levels	x		x		x			x		x	x**		x**
Study Procedures													
Medication Pill Count			x	x	x	x	x	x	x	x**	x**	x**	x**
Adverse Events	x	x	x	x	x	x	x	x	x	x**	x+	x**	x**
Study Termination										x^			x**

*Home pregnancy test permitted

^ Only for subjects not participating in OLE (Open-Label Extension)

**Only for subjects participating in OLE (Open-Label Extension)

+ For participants in OLE (Open-Label Extension) and those not participating in OLE

a. Pregnancy tests need to be done monthly in OLE (Open-Label Extension). Participants will be given home pregnancy test kits to take home.

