7 ASSESSMENTS

7.1 Screening/Baseline Assessment

Prior to enrollment, each participant will undergo a medical screen, be introduced to study procedures,

The SATURN Study [CONFIDENTIAL – DO NOT REDISTRIBUTE]

and undergo informed consent. Screening will be conducted within 30 days of baseline assessment. If any of the screening labs were performed as part of standard of care within 4 weeks of the screening, these labs will be used for screening.

If the patient qualifies and consents to participate, they will undergo baseline assessments. Baseline labs that were done within the previous 4 weeks will be accepted as baseline labs; if there are no labs for >4 weeks, these will be repeated. If any of the following baseline procedures were performed and documented in the medical chart at part of standard of care within 2 months of the baseline visit, these will be accepted as the baseline assessment: RHC, PFTs, 6MWDT, 12-Lead ECG.

All participants will start taking the study drug on the morning of Day 1, the day after the baseline assessment. All participants will follow up in person for assessments at Weeks 4, 12, and 24. Participants will also be contacted electronically and/or by telephone on Weeks 2, 8, 16, 20, 28. Participants will continue the study drug for 24 weeks with the final in person assessment at Week 24. A final follow-up electronically or by telephone will be performed at week 28 (4 weeks after treatment completion). If participants do not complete the 24 weeks of treatment for any reason, every effort will be made to conduct the Week 24 final assessment at the time of treatment termination and the participant will be followed until at least 4 weeks after stopping the study drug (longer if necessary to follow AEs). If the participants are enrolled in the open-label extension, they will be contacted by telephone on Weeks 26 and 36. A final in-person assessment will occur at Week 48.

Biological samples:

- Blood:
 - 6 ml blood for serum concentration of H01 and metabolites
 - 6 ml blood for serum HA level and biomarkers
 - 6 ml blood for CBC
 - 6 ml blood for CMP
- Urine:
 - Pregnancy test for females of child-bearing potential (serum pregnancy test may be substituted for urine)
- Exhaled breath condensate:
 - Concentration of HA levels, H01 and metabolites

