8.4 Possible Reasons for Discontinuation of Treatment

All reasons for discontinuation from study drug will be captured in study CRFs enabling for the ability to differentiate treatment discontinuation from study withdrawal. These include the following reasons:

- Completed 24 weeks of treatment of the blinded study or 48 week of the open-label extension
- Grade ≥ 3 Adverse Drug Reactions
- Withdrawal of consent
- Physician request

Investigators and study staff are reminded of the importance of participant retention in the case of treatment discontinuation and should take steps to prevent missing data that will be critical to the interpretation of the study results. Investigators and study staff should remind participants of the importance of continued participation in laboratory and clinical monitoring. Participants who discontinue study drug should continue follow-up when possible. This concept will be reinforced in the Informed Consent Form (ICF).

In the case of missing data for participant disposition for a randomized participant, a vital records search will be undertaken.

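### Section 5.3 keeps new PAH/PH treatment barred for about 4 weeks or more after study drug stops, with no exception for clinical worsening, although no scheduled blinded-phase efficacy measurement then remains

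*Combined protocol and SAP*

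**What the plan says.** Section 5.3 (Concomitant Medication) states: "Participants may not newly initiate PAH/PH treatment from the first dose of study drug (Baseline) through study termination". The sentence after it bars starting pulmonary rehabilitation "within 90 days prior to the first dose of study drug and until the end of the study". Both rules run to the end of the study rather than to the last dose.

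The protocol treats stopping drug and leaving the study as separate events. Section 8.4 has reasons for discontinuation captured on the case report forms, "enabling for the ability to differentiate treatment discontinuation from study withdrawal", and adds: "Participants who discontinue study drug should continue follow-up when possible". The schedule in Section 6 has its own row labelled "Study Termination".

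For someone who stops before completing 24 weeks, Section 7.1 says that "every effort will be made to conduct the Week 24 final assessment at the time of treatment termination" and that "the participant will be followed until at least 4 weeks after stopping the study drug (longer if necessary to follow AEs". For completers it says: "A final follow-up electronically or by telephone will be performed at week 28 (4 weeks after treatment completion". Section 1.2 gives the blinded study 28 weeks, of which 24 are on treatment.

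**The concern.** A bar on new background therapy is sound while study drug is being taken and efficacy is still to be measured. Without it, a new vasodilator could be mistaken for an effect of H01. That reason weakens once study drug has stopped and the last efficacy assessment has been made.

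The people affected are ill. Section 5.1 admits WHO functional class II to IV despite two or more treatment modalities. Section 9.6 counts worsening of an existing condition as an adverse event, and Section 9.14 keeps anyone who stopped drug for an adverse event in follow-up until the event settles or is stable. A participant who stops because PH is worsening is therefore held in the study by one rule and refused a new PH agent by another. What remains is withdrawal, which works against the retention aim of Section 8.4, or a deviation logged under Section 9.13. At stake are care and retention more than the PVR estimate.

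**Working it through.** No sample size, power or alpha figure bears on this point; Section 10.7 says that the 16 participants are not a powered number. The check compares the end of the bar with the end of study drug and with the last measurements due.

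**1. How long the bar outlasts study drug, read literally**

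- Completers outside the extension: the blinded study lasts 28 weeks and treatment 24 (Section 1.2), so 28 − 24 = 4 weeks, or 4/28 = 14% of the blinded study. Section 3.1 gives the follow-up as 30 days, hence "about" 4 weeks here.
- Early stoppers in the blinded phase: at least 4 weeks (Section 7.1), longer if adverse events are being followed, with no stated maximum.
- Extension completers: drug and study both end at Week 48, so 48 − 48 = 0 weeks.

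**2. Whether any section lifts the bar**

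- Section 9.7 allows drugs to relieve symptoms of abnormalities attributed to study drug. Its examples are for nausea, diarrhea and pain, and it names no PH agent.
- Section 9.14 lets the investigator stop study drug. It does not allow PH therapy to be started.
- The last paragraph of Section 5.3, on drugs taken for adverse events, is a recording rule.

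None is an exception for clinical worsening.

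**3. What is still to be measured once drug has stopped**

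- Right heart catheterizations: two are scheduled, at screening and Week 24. Section 7.1 moves the second to the time of stopping for early stoppers. After it, 2 − 2 = 0 remain.
- Other blinded-phase efficacy measures (mPAP, walk distance, questionnaires, serum HA, NT-proBNP): Section 4.2 defines them to Week 24, and Section 7.1 makes Week 28 a remote contact. Scheduled after the Week 24 or exit assessment: 0.
- Safety: at least one assessment, the adverse event review at Week 28. Section 9.6 collects events until about 30 days after the last dose.

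The columns of the schedule table appear shifted in the text available, so this step rests on Sections 4 and 7.1 and not on where the table's marks fall.

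**4. Whether there could be an agent to start**

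Section 5.1 names four modalities and requires at least two. At that minimum, 4 − 2 = 2 classes could be untried. This is a ceiling, since the criterion applies only where a modality is appropriate.

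**5. What could reach the primary endpoint**

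At 5:3, 16 participants split into 16 × 5/8 = 10 and 16 × 3/8 = 6. Section 10.6 uses complete cases. A participant who withdrew before the exit catheterization would cost 1 of 10 or 1 of 6 PVR changes (10% or 17% of an arm). The documents do not say how often this would happen.

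**The case against.** The strongest reply is that something is left to protect. Safety by CTCAE is the first secondary endpoint in Section 4.2. Events are collected off drug, attributed to study drug (Section 9.9) and summarized by arm (Section 10.4), and a new PH agent would cloud that attribution. This stands, and it is why the point is confined to efficacy. A reader might infer that the bar protects no endpoint at all; the documents do not support that. Still, Section 5.3 already requires new drugs to be recorded, and PH left to worsen produces adverse events of its own.

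Second, the exit assessment is promised only as a best effort. If catheterization is delayed, the bar still protects the primary endpoint. This stands too, so the bar should end at the assessment, with an exception where catheterization is not feasible.

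Third, a reader might count from an early stop to Week 28 or Week 48 and report a much longer bar. That does not hold. Section 8.4 asks for continued follow-up only where possible, and someone followed that long in the blinded phase would pass in-person visits at which efficacy could still be measured. In the extension, walk distance, quality of life, serum HA and NT-proBNP are secondary endpoints through Week 48, so the bar does protect something there.

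Fourth, the term that ends the bar is undefined, and the heading of Section 9.14 uses early termination for stopping drug, so a laxer reading is open. That is true, but it leaves the matter to each investigator.

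Last, the care harm is uncertain. Sections 1.3.1 and 1.3.2 call PAH agents ineffective or harmful in IPF with PH, and Section 5.3 does not forbid raising the dose of an existing agent. This limits the harm but does not remove it: the quoted view concerns IPF with PH, and the trial also enrolls Group 1 patients.

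**Conclusion.** The point holds on a literal reading of Section 5.3 and is minor. The bar runs about 4 weeks past the last dose for completers outside the extension, and at least 4 weeks for blinded-phase early stoppers. After the Week 24 or exit assessment it guards no scheduled blinded-phase efficacy measurement, though adverse events are still being collected. The conclusion assumes that the bar ends at study exit and not at the end of dosing, and, for early stoppers, that the exit assessment was actually done.

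A reader might infer a biased PVR result. The documents do not support that. The exit catheterization fits the end-of-treatment wording of Section 10.3, the number who would stop for worsening PH is not given, and any effect is unquantified and probably small. What remains is a conflict between care and retention that the protocol creates without need.

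**What to change.** In Section 5.3, state that:

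- the bar ends at the final efficacy assessment, which is Week 24 for those not entering the extension, or the Section 7.1 exit assessment with catheterization after permanent discontinuation;
- after permanent discontinuation, new PH therapy for clinical worsening may start at once if the exit catheterization is not feasible, with the start date recorded;
- the same rule applies to participants who stop early in the extension. Section 7.1 words its exit rule for the 24-week phase only, so say that their Week 48 efficacy measures are brought forward to stopping where feasible.

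In Section 10.3, add one sentence confirming that the exit catheterization supplies the end-of-treatment PVR.

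The cost is a few sentences. No form or participant is added, because Section 5.3 already has new drugs recorded. There are three downsides. Adverse events after new therapy starts will be harder to attribute to study drug. Some end-of-treatment values will fall before Week 24. Any catheterization or Week 48 extension value taken after new therapy must be flagged. The bar stays fully in force while study drug is being taken.

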6 SCHEDULE OF ASSESSMENTS

Schedule of Assessments for SATURN Trial

Visits	Screen		Active							FU			
	Screening	Baseline	Week 2	Week 4	Week 8	Week 12	Week 16	Week 20	Week 24	Week 26**	Week 28+	Week 36**	Week 48 **
Day ^a	0	1	14±3	28±3	56 ± 3	84±7	140 ± 7	168±7	196±7	210±3	224±3	280±7	364±7
Telephone or Email Contact			x		x		x	x		x**	x^	x**	
Informed Consent	x												
History and physical													
Medical history	x	x											
Symptom assessment/NYHA	x	x	x	x	x	x	x	x	x	x**	x+	x**	x**
Medications	x	x	x	x	x	x	x	x	x	x**	x+	x**	x**
Vital Signs & Weight	x		x		x			x			x**		x**
Physical Examination	x		x		x			x			x**		x**
EMPHASIS-10 / SGQ	x		x		x			x			x**		x**
General Testing													
Comprehensive Metabolic Panel	x		x		x			x		x	x**		x**
CBC	x		x		x			x		x	x**		x**
Pregnancy test (If Indicated) ^a	x		x	x*	x	x*	x*	x*	x	x**	x**	x**	x**
12-Lead ECG	x												
Endpoint assessment													
Right Heart Catheterization	x								x				
Serum & EBC hyaluronan	x		x		x			x		x	x**		x**
6 minute walk distance	x		x		x			x		x	x**		x**
NT-pro-BNP	x		x		x			x		x	x**		x**
PFT with ABG	x							x		x			
Inflammatory markers	x		x		x			x		x	x**		x**
Serum and EBC drug levels	x		x		x			x		x	x**		x**
Study Procedures													
Medication Pill Count			x	x	x	x	x	x	x	x**	x**	x**	x**
Adverse Events	x	x	x	x	x	x	x	x	x	x**	x+	x**	x**
Study Termination										x^			x**

*Home pregnancy test permitted

^ Only for subjects not participating in OLE (Open-Label Extension)

**Only for subjects participating in OLE (Open-Label Extension)

+ For participants in OLE (Open-Label Extension) and those not participating in OLE

a. Pregnancy tests need to be done monthly in OLE (Open-Label Extension). Participants will be given home pregnancy test kits to take home.

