3.1 Study Treatment

Participants will be randomized approximately 5:3 (Treatment:Placebo). Participants randomized to treatment will be given 800 mg oral H01 two times a day (total dose: 1600 mg/day). Participants randomized to placebo will receive oral tablet placebo (inactive ingredients) two times a day. Participants will be on treatment continuously for 24 weeks or 48 weeks if enrolled in the open-label extension. During the treatment period, participants will be monitored according to the schedule of assessments below. Participant a follow up will take place 30 days after the end of treatment at Week 24 if not enrolled in the open-label extension.

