4 ENDPOINTS

4.1 Primary Endpoint

- Change in pulmonary vascular resistance (PVR) measured by right heart catheterization (RHC) from baseline to end of treatment (Week 24) of the blinded study

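### From Week 16 the schedule's Day row runs 28 days late, so the printed Week 24 window for the primary catheterization (Day 189 to 203) leaves out Day 168, when 24 weeks of dosing end

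*Combined protocol and SAP*

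**What the plan says.** The Section 6 schedule gives every visit both a Week label and a study day with a tolerance. Weeks 2, 4, 8 and 12 are Day 14±3, 28±3, 56±3 and 84±7. Weeks 16, 20, 24, 26, 28, 36 and 48 are "140 ± 7 168±7 196±7 210±3 224±3 280±7 364±7". The RHC row is marked at Screening and Week 24 only.

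The text works in weeks. Section 7.1 states "All participants will start taking the study drug on the morning of Day 1" and "Participants will continue the study drug for 24 weeks with the final in person assessment at Week 24". Weeks 16 and 20 are remote contacts: "Participants will also be contacted electronically and/or by telephone on Weeks 2, 8, 16, 20, 28". For those who stop at Week 24, "A final follow-up electronically or by telephone will be performed at week 28 (4 weeks after treatment completion". Section 4.1 defines the primary endpoint as the change in pulmonary vascular resistance (PVR) on RHC "from baseline to end of treatment (Week 24) of the blinded study". Section 3.1 adds "Participants will be on treatment continuously for 24 weeks or 48 weeks if enrolled in the open-label extension" and, for those who do not extend, "follow up will take place 30 days after the end of treatment at Week 24".

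Section 9.6 closes adverse event (AE) recording at Day 196 and describes that day as no less than 30 days past the final dose.

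**The concern.** From Week 16 on, the two rows of the schedule give different dates for the same visit. For the telephone contacts this is untidy. For Week 24 it bears on the only measurement of the primary endpoint after baseline.

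- **Scheduling by the Day row.** If drug stops by the week count, the RHC comes 21 to 35 days after blinded treatment ends. It would then be off drug, or on open-label H01 if the extension had already started. If drug is instead continued up to the visit labelled Week 24, blinded dosing lasts about 28 weeks, not 24.
- **Scheduling by the Week label.** An RHC on Day 168 is on time but outside the printed window. Section 9.13 has all deviations logged, and Section 10.1 drops participants with major deviations from the per-protocol population without defining major. The primary analysis is in the ITT population, so this route touches only the secondary population.

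With 16 participants and complete-case analysis (Section 10.6), a few RHCs taken at the wrong time could move the arm means.

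**Working it through.** **Inputs.** Week labels, printed days and tolerances are from Section 6. The start of dosing (Day 1) and its length (24 weeks) are from Section 7.1. The AE cut-off (Day 196) is from Section 9.6.

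**Rule.** Day = 7 × week. This reproduces the plan's own entries up to Week 12: 7×2 = 14, 7×4 = 28, 7×8 = 56, 7×12 = 84.

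**The rest of the row.**

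| Week | 7 × week | Printed day | Printed window | Offset |
|---|---|---|---|---|
| 16 | 112 | 140 | 133–147 | +28 |
| 20 | 140 | 168 | 161–175 | +28 |
| 24 | 168 | 196 | 189–203 | +28 |
| 26 | 182 | 210 | 207–213 | +28 |
| 28 | 196 | 224 | 221–227 | +28 |
| 36 | 252 | 280 | 273–287 | +28 |
| 48 | 336 | 364 | 357–371 | +28 |

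No window from Week 16 on contains the day that its label means.

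**Where the slip occurs.** Week 12 to Week 16 is printed as 140 − 84 = 56 days, while the labels give (16 − 12) × 7 = 28. Every later printed step (28, 28, 14, 14, 56 and 84 days) agrees with its labels. There is one error, carried forward.

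**Week 24.** Twenty-four weeks from Day 1 are Days 1 to 168 (24 × 7 = 168). The printed window is 196 ± 7 = 189 to 203. Its edges lie 189 − 168 = 21 and 203 − 168 = 35 days after the end of treatment. Day 168 is the centre of the window printed for Week 20, a telephone contact. If dosing instead continued to the printed day, its length would be 196 / 7 = 28 weeks.

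**Does another origin rescue the row?** The table prints Baseline as Day 1, whereas Section 7.1 makes Day 1 the day after baseline. Shifting the start by one day moves the end of treatment to Day 169, still 189 − 169 = 20 days before the window opens. Counting from screening fails too: Screening is printed as Day 0, and Weeks 2 to 12 carry no offset.

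**Cross-check with Section 9.6.** Day 196 lies 196 − 168 = 28 days after Day 168. That roughly fits the section's description and supports a last dose at Day 168. If Day 196 were Week 24, AE recording would close as treatment ended. The match is not exact, since 28 days is 2 short of 30. For extension participants, dosing runs to 48 × 7 = Day 336, so a fixed Day 196 cannot follow their last dose.

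**Week 28 after correction.** 196 ± 3 = 193 to 199. A 30-day minimum fits inside it only if the last dose is by 199 − 30 = Day 169. A last dose on Day 175, the end of the corrected Week 24 window, would need contact on Day 205 or later.

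**The case against.** The strongest reply is that this is one slip in one table row and that the rest of the protocol settles the meaning. Sections 1.2, 4.1 and 10.3 tie the primary endpoint to the end of treatment, never to a study day. Section 7.1 schedules by week and brings the Week 24 assessment forward for anyone who stops early. No planned analysis uses the Day windows. There is one site, and the primary endpoint is not tested. The study operations manual, which is not among the documents, may carry the right days. All of this stands and limits how serious the point is. It does not make the row correct, and the row carries the visit windows that the protocol prints.

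Nor is it a fault of text extraction. Some assessment marks in the table look displaced, but the Day row has one value for each of its 13 columns, in a coherent sequence.

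Two stronger readings are tempting, and the documents do not support them.

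- **A reader might infer that the primary RHC will be taken off drug or on open-label H01.** That needs drug to stop or switch by the week count while the RHC is booked by the Day row. Using the Day row throughout gives about 28 weeks of blinded dosing instead. The open-label version also needs the extension to start before the RHC. No section says that extension drug is supplied before the Week 24 visit, and the first extension-only column is Week 26. That placebo participants move to H01 is itself an inference: Section 1.2 describes extension dosing only for the H01 arm, while Section 2.1 is more general. The placebo arm at 5:3 is 16 × 3/8 = 6 people, a ceiling on the number of placebo participants who could be affected and not an estimate.
- **A reader might infer that AEs go unrecorded for most of the extension.** That takes Day 196 literally, against the section's own explanation of it and against the schedule, where the Adverse Events row is marked through Week 48.

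**Conclusion.** The Day row is wrong as written. Seven of its 11 post-baseline entries are 28 days late because of one error. The consequential entry is Week 24, where the printed RHC window misses the end of 24 weeks' treatment by 21 days at its nearer edge. This rests on dosing from Day 1 for 24 weeks and on the Week labels being the intended timing, as the text consistently indicates. Any harm depends on staff having used the Day row, and nothing in the documents shows that they did.

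The row should be corrected because it governs the visit for the sole primary endpoint and the correction is almost free. It is not a flaw in the design or the analysis. The AE cut-off is a minor companion point: 2 days short of its stated interval for those who finish at Week 24, and unusable as a fixed day for those who extend.

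**What to change.** 1. In Section 6, change the Day entries for Weeks 16, 20, 24, 26, 28, 36 and 48 to 112±7, 140±7, 168±7, 182±3, 196±3, 252±7 and 336±7. The Week 24 window becomes Day 161 to 175. Leave the 24- and 48-week durations as they are.
2. Check any visit windows, calendars or database checks already built from the row. If visits have taken place, list the actual RHC date against the last blinded dose for each participant.
3. In Section 9.6, delete the fixed Day 196 and keep a stated interval after the last dose for all participants, including those in the extension. Either adopt the 4 weeks already in Sections 1.2 and 7.1, and align Section 3.1 with it, or keep 30 days and time the final contact from the last dose in place of the ±3-day window. Counting from the actual last dose is safer in both cases, since a last dose on Day 175 puts even the 4-week point at 175 + 28 = Day 203.

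The cost is seven table entries and a few words on the follow-up interval. Correcting the row adds no visit or procedure. The schedule shows no contact after Week 48, so applying the post-dose AE interval to extension participants may take one telephone call each. Section 9.6 already implies that period.
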